#### 11.2 SAMPLE SIZE

Sufficient patients will be screened for 18 patients to be enrolled into cohort A and 8 into cohort B of this open-label study. Patients withdrawn after first treatment with IMM-101 will not be replaced. No formal sample size calculation has been performed and the sample size is considered a sufficient and adequate number of patients to investigate the efficacy signals of IMM-101 combined with nivolumab in controlling advanced melanoma and to explore the safety profile of the combination therapy.

Page 80 of 98

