#### 11.7 PATIENT SELECTION FOR ANALYSES

# 11.7.1 Analysis Sets

The efficacy and tolerability endpoints will be evaluated using the Intent-to-treat (ITT) set, defined as all patients receiving at least one dose of IMM-101, irrespective of compliance with eligibility and other protocol criteria. This set will also define the Safety set.

In addition, a Per-protocol (PP) set, defined as ITT patients with no major protocol deviations and having complied with the treatment regimens of the combination therapy, will be used to evaluate further the efficacy of the combination therapy for the primary and secondary efficacy parameters.

The data for any enrolled patients who are not in the ITT set (i.e., who do not receive at least one dose of IMM-101) will be listed only.

Page 81 of 98

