3 SAMPLE SIZE

Sufficient patients will be screened for 18 patients to be enrolled into cohort A and 8 into cohort B of this open-label study. Patients withdrawn during the course of the

study will not be replaced. No formal sample size calculation has been performed and the sample size is considered a sufficient and adequate number of patients to investigate the efficacy signals of IMM-101 combined with nivolumab in controlling advanced melanoma and to explore the safety profile of the combination therapy.

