5.6 Protocol Deviations

Prior to database lock, the Immodulon Medical Monitor will review all individual deviations and classify them as major or minor during a data review meeting. Decisions arising from the data review meeting will be documented in the minutes and will be approved by the Immodulon Medical Monitor (on behalf of Immodulon) and the Project Statistician. Major deviations considered having a serious impact on the efficacy results will lead to the relevant subject being excluded from the PPS.

Major protocol deviations may include but are not limited to:

- Prior treatment for naïve disease (Cohort A only).
- Active brain metastases or leptomeningeal metastases (Cohort A only).
- Subject enrolled under Protocol Version 1.0 did not receive the minimum 4 doses of anti-PD-1 therapy before progression (RECIST 1.1) was documented and/or more than 8 weeks had elapsed between the last dose of anti-PD-1 therapy and the start of Screening (Cohort B only).
- Subject enrolled under Protocol Version 2.0 did not receive the minimum 3 doses of anti-PD-1 given as a monotherapy or the minimum 2 doses of anti-PD-1 given in combination regimes before progression (RECIST 1.1) was documented and/or more than 12 weeks but less than 6 weeks had elapsed between the last dose of anti-PD-1 therapy and the start of IMM-101 administration (Cohort B only).
- Subject has not received at least one dose of both IMM-101 and nivolumab.
- Subject does not have at least 1 measurable lesion by CT/MRI (RECIST 1.1) at baseline assessment and/or at least one post baseline measurable scan (whether or not scheduled).
- Subject has received on-study prohibited medications considered likely to have had an impact on the efficacy of study medication.

Protocol deviations which can be attributed to the COVID-19 pandemic will be entered into the eCRF with a comment indicating that the deviation is due to COVID-19. No specific COVID-19 category has been added to the eCRF as COVID-19 is a reason for a deviation and not a deviation in itself. However, these COVID-19-related deviations may be summarised under a separate category of COVID-19 if sufficient in

number and in addition to being identified in data listings, as determined at the data review meeting.

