5.13 EFFICACY EVALUATION

5.13.1 Primary Endpoint

The primary endpoint will be analysed using the ITT set and repeated for the PPS for Cohort A only.

Primary Analysis

The primary efficacy endpoint of the study is the ORR calculated from the BOR of subjects as assessed by RECIST 1.1.

The investigator response will be entered into the Response Assessment (RECIST 1.1) page of the electronic Case Report Form (eCRF) at each scan assessment to be used in the derivation of BOR.

A confirmed response will be used in the derivation of BOR. A confirmed response is defined as a response obtained from a scan repeated at least 4 weeks following a scan with designation of complete response (CR) or partial response (PR), as defined using Table 3 of RECIST 1.1. In addition, the following approaches will be taken:

- Where a confirmatory assessment is non-evaluable (NE) but the subsequent scan maintains the same response/progression, the response/progression will be considered confirmed (e.g. PR-NE-PR).
- Subjects without a confirmed response of CR or PR will have their next best response (stable disease (SD) or otherwise progressive disease (PD)) assigned as their BOR.
- Subjects without a BOR assessment, such as those with no post-baseline responses or only NE responses, will be assumed to have a BOR of PD using a worst-case approach.

For Cohort A, BOR is defined as the best confirmed response designation, recorded from the first post-baseline scan until and including the last scan on study for each subject.

For Cohort B, BOR is defined as the best confirmed response designation, recorded from the first post-baseline scan until and including the last scan on study for each subject for those receiving IMM-101 and nivolumab, or the last scan performed prior to treatment with ipilimumab. No scan performed once ipilimumab treatment commences will be included.

All scans within these periods, whether scheduled or unscheduled, will be evaluated for overall response.

ORR is calculated as the number of subjects with a BOR of confirmed CR or PR divided by the number of subjects in the analysis set. ORR is calculated for each cohort separately.

Summaries of BOR (best confirmed overall response designation)

The BOR will be summarised for each cohort. The ORR and accompanying exact binomial 95% confidence intervals (CI) will also be presented.

Listings of lesions assessments and BOR

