5.13.2.2 OS and OS at 1 Year for Cohorts A and B

OS and OS at one year will be analysed using the ITT set and analysis will be repeated for the PPS for Cohort A only.

OS is defined in months as the time between Visit 1 and the date of death from any cause (date of death – date of Visit 1 + 1).

OS will be calculated for the entire study duration where subjects without a death date will be right censored at the date the subject was last known to be alive (during or post study). Post-study survival information is collected until database lock, for subjects completing or withdrawing from the study.

OS will also be calculated for subjects at one year, where subjects without a death date will be right censored on the date of Visit 1 + 365 days.

Summaries of OS

Descriptive statistics will be presented for OS for the whole study period and repeated for OS at one year. The number and percentage of subjects that are censored will be summarised, along with KM estimates for the 25th, 50th and 75th percentiles for both OS and OS at one year and corresponding 95% CIs for each. OS and OS at one year will also be presented graphically using a KM plot. The proportion of subjects alive at 3 monthly intervals will also be presented.

Survival status and death details (during or post study) will be listed for each subject.

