6 CHANGES FROM THE PROTOCOL PLANNED ANALYSIS

1. The Cohort A interim data review will be conducted when the first 11 Cohort A subjects enrolled into the study have had the opportunity for 1 year on study. The Cohort B interim data review will be conducted when the first 5 Cohort B subjects enrolled into the study have had the opportunity for 6 months on study. Any further enrolled Cohort A/B subjects will not be included in the data reviews of efficacy, but their AE data will be included in the data reviews of safety.
2. The data cut-off for the interim data reviews has been clarified. This specifies the scan assessments included for each interim data review are derived using dates for each subject and not the nominal scan assessments.
3. Clarification has been made to the definition of the PPS. The definition requires subjects to have complied with the treatment regimen, but this is naturally implied by the definition given any non-compliance would be a protocol deviation.
4. Tables will be produced for the PP analysis set in addition to the ITT analysis set for Cohort A only. Due to the small size of Cohort B, there will be no separate set of tabulations for the PP set in Cohort B. Analysis set assignment and protocol deviations will still be listed for all subjects.

5. Clarification has been made to the requirement for subgroups to be summarised provided the respective subgroup size is at least 33% but less than the total size of the ITT set for Cohort A, and at least 50% but less than the total size of the ITT set for Cohort B.

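### SAP 5.6 allows Cohort A patients with no post-baseline scan to be excluded from the Per-Protocol Set, so early deaths and clinical failures may leave the supportive ORR, PFS and OS analyses because of their outcome

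*SAP*

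**What the plan says.** SAP 5.3 defines the PPS as the ITT patients with no major protocol deviations. SAP 5.6 gives examples of major deviations. One is a patient without a measurable lesion on CT or MRI "at baseline assessment and/or at least one post baseline measurable scan (whether or not scheduled". The list is introduced as illustrative and open-ended. The sponsor's Medical Monitor classifies each deviation at a data review meeting before database lock, and the decisions are approved jointly with the Project Statistician. SAP 5.6 then excludes patients whose major deviations are judged to affect the efficacy results seriously; SAP 5.3 carries no such qualifier.

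The PPS is tabulated for Cohort A only, for ORR (SAP 5.13.1), PFS (5.13.2.1) and OS, where "analysis will be repeated for the PPS for Cohort A only" (5.13.2.2).

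On the ITT set, a patient with no post-baseline response "will be assumed to have a BOR of PD using a worst-case approach" (SAP 5.13.1), and a death without reported progression is a PFS event on the date of death (5.13.2.1).

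Protocol 5.1 and 5.3 put the first scheduled Cohort A scan at Week 12 (±7 days) and allow unscheduled scans. Protocol 8.3 asks for a scan at the withdrawal/end-of-study visit if more than 8 weeks have passed since the last one and progression is not already documented.

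On compliance, Protocol 11.7.1 describes the per-protocol population as "ITT patients with no major protocol deviations and having complied with the treatment regimens of the combination therapy". The SAP definition keeps only the first condition. SAP Section 6, item 3, says of the second that "this is naturally implied by the definition given any non-compliance would be a protocol deviation".

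**The concern.** A per-protocol set is meant to remove patients whose treatment or conduct departed from the protocol. A Cohort A patient who dies in Week 6 has departed from nothing, yet meets the scan criterion. Membership of the PPS is then partly decided by what happened after treatment began.

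The SAP has sensible rules for such patients: no post-baseline response becomes PD, and a death is an event. Those rules cannot act on a patient who has already been taken out of the set. The patients at risk of removal for this reason are non-responders and early deaths, so their loss makes the combination look better.

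This matters because the study is uncontrolled and both documents say its results will be compared with published nivolumab data. The protocol cites an ORR of 44% for nivolumab in treatment-naive patients. A PPS estimate could sit above that figure through a smaller denominator alone.

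**Working it through.** **No planned figure to reproduce.** SAP Section 3 states that "No formal sample size calculation has been performed". Planned enrolment is given in Protocol 11.2: "Sufficient patients will be screened for 18 patients to be enrolled into cohort A and 8 into cohort B". Neither the number of responders nor the number of patients without any scan is given, so both are assumed below and shown over a range.

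**Who is affected.** Only Cohort A patients with no post-baseline scan of any kind. The end-of-study scan rescues some of them. Baseline imaging may be up to 21 days before the first dose, and the end-of-study visit is 28±7 days after the last IMM-101 dose.
- Stopped after the first dose: the longest gap is 21 + 35 = 56 days, which is exactly 8 weeks. The trigger is more than 8 weeks, so no scan is required within these windows.
- Stopped after the Week 2 dose: the longest gap is 21 + 14 + 35 = 70 days, so a scan can be required.
- A patient who has died cannot be scanned.

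**ORR.** With r responders among 18 and k unscanned patients removed, PPS ORR = r/(18 − k). ITT ORR stays at r/18. Assume r = 8, close to the cited 44%; intervals are exact 95%.

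| k removed | PPS ORR | 95% CI |
|---|---|---|
| 0 | 8/18 = 44.4% | 21.5 to 69.2 |
| 1 | 8/17 = 47.1% | 23.0 to 72.2 |
| 2 | 8/16 = 50.0% | 24.7 to 75.3 |
| 3 | 8/15 = 53.3% | 26.6 to 78.7 |

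With r = 7 the same steps give 38.9%, 41.2%, 43.8% and 46.7%. With r = 9 they give 50.0%, 52.9%, 56.2% and 60.0%. SAP Section 4 reports 11 Cohort A patients when recruitment was suspended. If the cohort stayed at 11 with an assumed 5 responders, ORR would go from 5/11 = 45.5% to 5/10 = 50.0% with one patient removed and 5/9 = 55.6% with two.

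**One-year OS.** Assume 5 deaths by one year among 18 and no censoring, so 13 survivors. PPS one-year OS = 13/(18 − k), where k of the deaths precede any scan and are removed: 13/18 = 72.2%, 13/17 = 76.5%, 13/16 = 81.25%, 13/15 = 86.7% for k = 0, 1, 2, 3.

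**PFS.** An early death without a scan is an ITT event and is lost if the patient is removed. An unscanned patient who does not die is censored at the first post-Screening visit in the ITT analysis, so removing that patient hardly changes the PFS curve. The PFS effect therefore comes from deaths.

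**How likely is k ≥ 1?** If each patient independently has probability p of no post-baseline scan, the chance of at least one among 18 is 1 − (1 − p)^18. For assumed p of 3%, 5%, 10% and 15% this is 42%, 60%, 85% and 95%.

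**The case against.** The strongest reply is that nothing here is automatic. The list in SAP 5.6 is permissive, the decision is taken and minuted before database lock, and a missing scan caused by death could be classed as minor or as having no serious efficacy impact. That is right, and it is why the point is that such patients may be removed. It is only partial protection: the study is open-label, SAP 5.3 has set membership agreed once all study data are available, and 5.3 and 5.6 differ on whether every major deviation excludes.

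A reader might infer that every death or clinical failure before Week 12 leaves the PPS, or that PPS survival must be 100% until about Week 11. The documents do not support either. Any scan satisfies the criterion, including an unscheduled or end-of-study one, and a patient scanned early who then dies remains a PPS death.

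A reader might also infer that the SAP has silently dropped the compliance condition, so that barely treated patients must stay in. That goes too far. The change is declared in SAP Section 6, the deviation list is not exhaustive, and serious non-compliance could be classed as major. A short course ended for progression or toxicity is also not necessarily non-compliance. What remains is a note: the stated justification is incomplete, because only major deviations exclude, the only listed example about receipt of study drug is at least one dose of each, and no compliance threshold is given.

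Finally, the consequences are limited. The PPS is supportive, the ITT analysis keeps these patients, all endpoints are descriptive, reasons for exclusion from each set are listed, and the confidence intervals above overlap almost completely.

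**Conclusion.** The point holds in this limited form. As worded, the scan criterion allows PPS membership in Cohort A to depend on outcome, and for patients whose scan is missing because they died or failed clinically the bias runs in favour of the combination. Under the assumed 8 responders of 18, each removed patient adds about 3 percentage points to the PPS ORR. Under the assumed 5 deaths by one year, each removed early death adds about 4 to 5 points to one-year OS. If nobody lacks a scan, or the reviewers decline to exclude such patients, the effect is zero. The primary ITT results do not change. This is a cheap improvement to a supportive analysis, worth making because that analysis will be read beside published single-agent figures.

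**What to change.** In SAP 5.6, delete the post-baseline-scan part of the measurable-lesion bullet as a ground for leaving the PPS. Alternatively, keep it but exempt patients whose scan is missing because of death, progression or toxicity. Either way, state that these patients stay in the PPS with BOR = PD and that their deaths count as PFS and OS events, as in the ITT analysis. Bring 5.3 and 5.6 into line on whether every major deviation excludes, or only those with serious efficacy impact.

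As a minor addition, state what degree of non-compliance counts as major for the PPS, or say that no threshold is applied.

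The cost is SAP wording only, with no new data or procedures. PPS figures may come out slightly less favourable.

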5.7 Background and Demographic Characteristics

5.7.1 Demography

Demographic characteristics (age, sex and race) and body measurements (height, weight and body mass index (BMI)) collected at Screening will be summarised.

Age is calculated in years from the date of informed consent.

BMI is calculated as (weight (kg)/height (m)²).

All subject demographic data will be listed.

5.7.2 Informed Consent

Informed consent details will be listed including the date of informed consent, the protocol version enrolled under, date and confirmation of consent for biopsy samples and the visit and date of the new protocol version if applicable.

5.7.3 Baseline Disease Status

The following baseline information about melanoma will be summarised.

- The time since diagnosis of melanoma will be calculated in months from the date of diagnosis to the first administration of IMM-101 (date of diagnosis – date of first administration of IMM-101 + 1)/30.4375.
- Number staging (III or IV).
- M staging (M0, M1a, M1b, M1c or M1d).
- Site of melanoma (skin, mucosa or unknown).
- Eastern Cooperative Oncology Group (ECOG) performance status, see Section 5.15.10 for information on ECOG.
- BRAF status (wild type or mutant).
- PD-L1 status for Cohort A only (positive/negative or indeterminate).

All information related to baseline disease status will be listed.

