5.12 Exposure and Compliance

An exposure summary will include the time on study, the overall exposure of each of IMM-101, nivolumab and ipilimumab and the total dose exposure of nivolumab. The number of doses of IMM-101, and whether they were full or half doses will also be summarised.

The time on study will be calculated in months as (date of completion/withdrawal - date of first IMM-101 administration + 1)/30.4375.

Overall exposure to each of IMM-101, nivolumab and ipilimumab will be calculated in months as (date of last administration – date of first administration + 1)/30.4375.

Total nivolumab exposure will be calculated in mg across the duration of the subject's participation as the sum of the total dose administered at each nivolumab dosing visit for each subject.

Compliance will be summarised for IMM-101, nivolumab and ipilimumab separately for each visit.

For IMM-101, the number of subjects receiving treatment and whether these were full or half doses, the number of subjects not dosed, the reason for not dosing, the number of subjects with delayed dosing and the reasons for the delay will be summarised.

For nivolumab, the number of subjects receiving the infusion and the reasons if they did not receive the infusion, the number of subjects with delayed infusion and reasons for delayed infusion, the dosing regimen chosen and whether the regimen was modified will be summarised. The number of subjects who received less than, more than or exactly the planned dose will also be summarised.

For ipilimumab, the number of subjects receiving the infusion and the reasons why they received the infusion will be summarised. For each of the four infusions, the

number of subjects with delayed infusion and reasons for delayed infusion and the number of subjects who received less than, more than or exactly the planned dose will also be summarised.

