5.13.2 Secondary Endpoints

5.13.2.1 PFS Assessed by RECIST 1.1 for Cohorts A and B

PFS will be analysed using the ITT set and analysis will be repeated for the PPS for Cohort A only.

PFS is defined in months as the time between Visit 1 and the first confirmation of progression using RECIST 1.1, or death from any cause (whichever occurs first) (date

of first progression or death – date of Visit 1 + 1). Progression is determined by the investigator using the CT or MRI scan (scheduled or unscheduled) or death due to any cause. Subjects who die without reported progression will be considered to have progressed on the date of their death.

The following censoring rules will apply:

- Subjects who did not progress or die will be right censored on the date of their last evaluable tumour assessment.
- Subjects who did not have any on-study tumour assessments (scans) and did not die will be right censored on their date of first post-Screening visit. Note that this definition is consistent with that used for [Checkmate 067](#)².
- Subjects who remain on study following radiotherapy or other prohibited treatment will be censored at their last scan assessment prior to the intervention therapy.
- Subjects in Cohort B who change therapy to IMM-101 + ipilimumab without documented progression by RECIST 1.1 will be censored at the date of their last evaluable tumour assessment prior to this change in therapy.

Summaries of PFS

Descriptive statistics will be presented for PFS. The number and percentage of subjects that are censored will be summarised, along with KM estimates for the 25th, 50th and 75th percentiles of PFS and corresponding 95% CIs. PFS will also be presented graphically using a KM plot. The proportion of subjects who have not progressed or died at three monthly intervals will also be presented.

A time to event listing will present the milestones required for calculation of each time to event efficacy parameter.

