5.13.3.2 Duration of Response Assessed by RECIST 1.1 for Cohorts A and B

Duration of response will be analysed using the ITT set and only subjects who have a documented response of CR or PR will be included.

Duration of response is calculated as the time in months from the date of first documented response of CR or PR per RECIST 1.1 until the date of documented PD per RECIST 1.1 or until the date of death due to any cause (date of death or PD – date of documented response + 1). All scans are considered, whether scheduled or unscheduled, in the determination of response and confirmed responses are not required.

Subjects who neither progress nor die will be right censored on the date of their last tumour assessment. For Cohort B subjects who change treatment to IMM-101 and ipilimumab, only responses evaluated until the point of this change in therapy are included.

Summaries of duration of response

Descriptive statistics will be presented for duration of response. The number and percentage of subjects that are censored will be summarised, along with KM estimates for the 25th, 50th and 75th percentiles for the duration of response and corresponding

95% CIs. The proportion of subjects who have not progressed or died following a complete or partial response at three monthly intervals will also be presented.

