5.13.3.3 Time to Response Assessed by RECIST 1.1 for Cohorts A and B

Time to response will be analysed using the ITT set and only subjects who have a documented response of CR or PR will be included.

Time to response is calculated as the time in months from Visit 1 to the first documented response of CR or PR per RECIST 1.1 (date of documented response – date of Visit 1 + 1). All scans are considered, whether scheduled or unscheduled, in the determination of response and confirmed responses are not required.

For Cohort B subjects who change treatment to IMM-101 and ipilimumab, only responses evaluated until the point of this change in therapy are included.

Summaries of time to response

Descriptive statistics will be presented for time to response. KM estimates for the 25th, 50th and 75th percentiles for the time to response and corresponding 95% CIs will be presented. The proportion of subjects who have not achieved complete or partial response at 3 monthly intervals will also be presented.

5.13.3.4 Disease Control Assessed by RECIST 1.1 for Cohort B from Week 14 Onwards

Disease control will be analysed using the ITT set for Cohort B only.

Disease control is defined as a subject with a response of CR, PR or SD as per RECIST 1.1. Confirmed responses are not required.

SD determination requires a minimum scan time of 9 weeks from the first administration of IMM-101. Therefore, the first scan to be considered for this determination is Week 14. If unscheduled scans take place earlier than Week 14 but later than Week 9, they will be used for determination of SD for disease control at Week 14. For further information on the scan windows see Section 5.2.4 of this SAP.

Disease control is assessed at each scheduled scan assessment from Week 14 until the end of the study. For subjects who change treatment to IMM-101 and ipilimumab, only responses evaluated until the point of this change in therapy are included.

Disease control rate is calculated as the number of subjects with disease control divided by the number of subjects in the analysis set.

Summaries of Disease Control

The number of subjects with controlled disease and the number without controlled disease will be summarised together with the disease control rate for each scheduled scan assessment. The binomial 95% CIs will also be presented.

Disease control will be listed for each subject in Cohort B for each Visit.

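### SAP 5.7.3 subtracts the dates in the wrong order, so time since diagnosis comes out negative; separately, four efficacy times are stated in months but their formulas lack the day-to-month divisor

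*SAP*

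**What the plan says.** **Time since diagnosis.** SAP 5.7.3 says this is "calculated in months from the date of diagnosis to the first administration of IMM-101". The formula that follows is "date of diagnosis – date of first administration of IMM-101 + 1)/30.4375".

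**Efficacy times.** Four derivations name months as the unit and then give a formula with no divisor:

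- PFS (SAP 5.13.2.1): "PFS is defined in months as the time between Visit 1 and the first confirmation of progression using RECIST 1.1", with the formula ending "of first progression or death – date of Visit 1 + 1".
- OS (SAP 5.13.2.2): defined in months, formula "date of death – date of Visit 1 + 1".
- Duration of response (SAP 5.13.3.2): a time in months, formula "date of death or PD – date of documented response + 1".
- Time to response (SAP 5.13.3.3): a time in months, formula "date of documented response – date of Visit 1 + 1".

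**The form used elsewhere.** SAP 5.12 puts the later date first and includes the divisor. Exposure is "date of last administration – date of first administration + 1)/30.4375", and time on study follows the same pattern.

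SAP 5.2 and its subsections give no general day-to-month conversion; SAP 5.2 leaves parameter-specific derivations to the individual sections. SAP section 6 does not mention the point.

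**The concern.** There are two separate slips.

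In SAP 5.7.3 the divisor is present but the order of the dates is reversed. Protocol 6.1 requires a histologically confirmed diagnosis for entry, so diagnosis precedes dosing and the difference is negative. Adding 1 to a negative number moves it towards zero, so the size is wrong as well as the sign.

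In the four efficacy formulas the order is right but the divisor is missing, so the printed arithmetic does not produce the stated unit.

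Time since diagnosis is a summarised baseline characteristic. PFS and OS are the two secondary efficacy endpoints; duration of response and time to response are exploratory. For all four, the SAP calls for Kaplan-Meier quartiles with 95% confidence intervals and proportions at three-monthly intervals. The objectives also call for comparison with published nivolumab data, so the unit of these times should be unambiguous.

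**Working it through.** **Inputs.** The formulas are those in SAP 5.7.3, 5.12 and 5.13. The intervals below are illustrative and assumed, although the week numbers are scan or visit weeks from the protocol schedule. The documents report no result for these derivations, so there is no plan figure to reproduce.

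**Reference form.** The divisor is the mean month: 365.25 / 12 = 30.4375. The SAP 5.12 exposure formula for first dose at Week 0 and last dose at Week 76 (532 days) gives (532 + 1) / 30.4375 = 17.51 months, a sensible value.

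**Time since diagnosis.** Let d be the number of days from diagnosis to first dose.

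- As written: (-d + 1) / 30.4375
- Dates reversed: (d + 1) / 30.4375

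| d (days) | As written (months) | Dates reversed (months) |
|---|---|---|
| 0 | 0.033 | 0.033 |
| 1 | 0 | 0.066 |
| 2 | -0.033 | 0.099 |
| 30 | -0.95 | 1.02 |
| 365 | -11.96 | 12.02 |
| 730 | -23.95 | 24.02 |
| 1826 | -59.96 | 60.02 |

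The written form is negative whenever d is 2 or more. Taking its absolute value gives (d - 1) / 30.4375. That is short of (d + 1) / 30.4375 by 2 / 30.4375 = 0.066 months, or two days, whatever the value of d (for d of 1 or more).

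**Efficacy times.** Let d be the number of days elapsed between the two dates.

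- As written: d + 1
- With divisor: (d + 1) / 30.4375

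| Example | d | As written | With divisor (months) |
|---|---|---|---|
| Progression or first response at Week 12 | 84 | 85 | 2.79 |
| Response at Week 12, progression at Week 52 | 280 | 281 | 9.23 |
| Death 365 days after Visit 1 | 365 | 366 | 12.02 |
| Event at Week 78 | 546 | 547 | 17.97 |

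The two columns differ by the constant factor 30.4375.

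The one-year example counts days elapsed from Visit 1. SAP 5.2.2 calls Visit 1 Day 0 but also sets the first dosing date as Study Day 1. If day 365 means Study Day 365, the elapsed time is 364 days, and the pair becomes 365 and 365 / 30.4375 = 11.99.

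**The case against.** The strongest reply concerns the four efficacy times. Each derivation names months in its own sentence. The bracket can be read as supplying the two dates and the +1 convention, with the conversion left to the 30.4375 printed elsewhere in the same SAP; no competing conversion appears. SAP section 1 places the table, listing and figure shells in a separate document that is not available here, so a conversion stated there cannot be ruled out. This largely stands. The wording makes the intended unit clear, and the fault is that formula and unit disagree.

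A reader might infer that the SAP directs PFS and OS to be reported in days under a months label, with results about 30 times too large and the three-monthly proportions read at the wrong times. The documents do not support that. It would happen only if a programmer ignored the stated unit and the SAP 5.12 pattern, and then accepted implausible values in a study with at most 18 months of treatment.

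A reader might also infer that the efficacy conclusions are at risk. They are not. A constant scale factor leaves unchanged who has an event, who is censored, the order of the times and the shape of the Kaplan-Meier curve. ORR uses none of these formulas. Time since diagnosis defines none of the subgroups in SAP 5.2.8, and the study is descriptive, with no hypothesis testing.

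None of this answers the reversed subtraction in SAP 5.7.3. Nothing in the documents corrects it, and a unit conversion in the shells would not do so.

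**Conclusion.** The point holds as a minor correction in two parts.

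1. SAP 5.7.3 is a stated derivation rule that gives a wrong result. Followed exactly, it is negative for any diagnosis two or more days before first dose, and removing the sign still leaves it two days short. That it affects essentially every patient rests on the assumption that a histologically confirmed diagnosis is in place at least two days before dosing, which the eligibility and screening process makes close to certain. The consequence is limited to one descriptive baseline row.
2. The formulas for PFS, OS, duration of response and time to response are inconsistent with their stated unit. Taken literally they return days, 30.4375 times the value in months. The consequence is limited to the scale of the reported times, and it arises only if the brackets are programmed without regard to the sentences around them.

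**What to change.** - In SAP 5.7.3, reverse the dates: date of first IMM-101 administration minus date of diagnosis, plus 1, all divided by 30.4375.
- In SAP 5.13.2.1, 5.13.2.2, 5.13.3.2 and 5.13.3.3, divide each bracketed formula by 30.4375. Alternatively, state once in SAP 5.2 that times in months are days divided by 30.4375.
- Check that the shells use the same unit and conversion.

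The cost is five small text corrections, or two if the conversion is stated once. Design, data collection, endpoints and censoring rules do not change.
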